9.10 Other aspects

Not applicable.

10. Protection of human subjects

Data on patients and physicians is anonymized, as are the providers and the sickness funds, before data is made available to the HRI. Therefore, this classifies it as exempt for IRB approval.

The study will be conducted in accordance with legal and regulatory requirements, as well as with scientific purpose, value and rigor and follow generally accepted research practices such as Good Pharmacoepidemiology Practices (GPP) issued by the International Society for Pharmacoepidemiology (ISPE), the International Society for Pharmacoeconomics and Outcomes Research (ISPOR) guidances, Pharmaceutical Research and Manufacturers Association (PhRMA) guidelines and similar standards.

11. Management and reporting of adverse events/adverse reactions

As per the EMA Guideline on Good Pharmacovigilance Practices (Module VI–Management and reporting of adverse reactions to medicinal products), for non-interventional study designs that are based on secondary use of data, individual reporting of adverse reactions is not required.

As per the EMA Guideline on Good Pharmacovigilance Practices (Module VI–Management and reporting of adverse reactions to medicinal products), for non-interventional study designs that are based on secondary use of data, individual reporting of adverse reactions is not required. Reports of adverse events/reactions will be summarized in the study report (European Medicines Agency 2012).

12. Plans for disseminating and communicating study results

The study will be posted on clinicaltrials.gov. The results will be presented in form of a study report and separately in form of a MS-PowerPoint presentation in English following the STROBE checklist [von Elm et. al 2008]. The results of the study are considered for publication and will follow the International Committee of Medical Journal Editors [ICMJE 2015] guidelines. In addition, communication in appropriate scientific meetings will be considered.

13. List of references

1. Camm AJ, Kirchhof P, Lip GYH, Schotten U, Savelieva I, Erns S, u. a. Guidelines for the management of atrial fibrillation. *Eur Heart J*;
2. Heeringa J, Kuip DAM van der, Hofman A, Kors JA, Herpen G van, Stricker BHC, u. a. Prevalence, incidence and lifetime risk of atrial fibrillation: the Rotterdam study. *Eur Heart J*. 1. April 2006;27(8):949–53.

Annex 1. List of stand-alone documents

None.

Annex 2. Tables

Table 3 – Phenprocoumon PZN codes

Description		Pack size	PZN
FALITHROM 1,5 mite Filmtabletten	20	St	972890
FALITHROM 1,5 mite Filmtabletten	100	St	972915
FALITHROM Filmtabletten	20	St	3011932
FALITHROM Filmtabletten	20	St	4421721
FALITHROM Filmtabletten	50	St	4421738
FALITHROM Filmtabletten	100	St	4421744
MARCOUMAR Tabletten	50	St	3352194
MARCOUMAR Tabletten	100	St	3352202
MARCOUMAR Tabletten	50	St	4334620
MARCOUMAR Tabletten	100	St	4334637
MARCOUMAR Tabletten	100	St	9726170
MARCOUMAR Tabletten	50	St	4958705
MARCOUMAR Tabletten	100	St	4958711
MARCOUMAR Tabletten	100	St	4386479
MARCUMAR Tabletten	14	St	5541315
MARCUMAR Tabletten	30	St	1300649
MARCUMAR Tabletten	49	St	5541321
MARCUMAR Tabletten	56	St	7768135
MARCUMAR Tabletten	92	St	7768170
MARCUMAR Tabletten	98	St	5541338
MARCUPHEN-CT 3 mg Tabletten	20	St	7636008
MARCUPHEN-CT 3 mg Tabletten	50	St	7636014
MARCUPHEN-CT 3 mg Tabletten	98	St	6588626
MARCUPHEN-CT 3 mg Tabletten	100	St	7636020
PHENPRO AbZ 3 mg Tabletten	98	St	6811219
PHENPRO AbZ 3 mg Tabletten	100	St	2059517
PHENPRO ratiopharm 3 mg Tabletten	20	St	4582128
PHENPRO ratiopharm 3 mg Tabletten	50	St	4582134
PHENPRO ratiopharm 3 mg Tabletten	98	St	6575233
PHENPRO ratiopharm 3 mg Tabletten	100	St	4582140
PHENPROCOUMON acis 3 mg Tabletten	20	St	10269507
PHENPROCOUMON acis 3 mg Tabletten	50	St	10269513
PHENPROCOUMON acis 3 mg Tabletten	100	St	10269542
PHENPROGAMMA 3 Tabletten	14	St	9404207
PHENPROGAMMA 3 Tabletten	20	St	2704892
PHENPROGAMMA 3 Tabletten	50	St	2704900
PHENPROGAMMA 3 Tabletten	100	St	2704917
MARCOUMAR Tabletten	100	St	8874891
MARCOUMAR Tabletten	100	St	3352202
MARCOUMAR Tabletten	50	St	4334620
MARCOUMAR Tabletten	100	St	4334637
MARCOUMAR Tabletten	100	St	9726170
MARCOUMAR Tabletten	50	St	4958705

MARCOUMAR Tabletten	100	St	4958711
MARCOUMAR Tabletten	100	St	4386479
MARCOUMAR Tabletten	50	St	8874885
MARCOUMAR Tabletten	2X25	St	3422256
MARCOUMAR Tabletten	100	St	3422262
MARCOUMAR Tabletten	50	St	4386462
MARCOUMAR Tabl.	50	St	1835787
MARCOUMAR Tabl.	100	St	1837390
MARCOUMAR Tabl.	50	St	4446773
MARCOUMAR Tabl.	100	St	4446796
MARCOUMAR Tabl.	50	St	6969475
MARCOUMAR Tabl.	100	St	6969481
MARCOUMAR Tabl.	20	St	2499417
MARCOUMAR Tabl.	50	St	2021408
MARCOUMAR Tabl.	100	St	3215540

Table 4 – Xarelto® PZN codes

Description	Pack size		PZN
XARELTO 2,5 mg Filmtabletten	1X10X10	St	8461290
XARELTO 2,5 mg Filmtabletten	1X28	St	9647915
XARELTO 2,5 mg Filmtabletten	1X30	St	8717186
XARELTO 10 mg Filmtabletten	5	St	9154791
XARELTO 10 mg Filmtabletten	5	St	2088536
XARELTO 10 mg Filmtabletten	10	St	5995074
XARELTO 10 mg Filmtabletten	10	St	9721534
XARELTO 10 mg Filmtabletten	10	St	7799012
XARELTO 10 mg Filmtabletten	10	St	7610606
XARELTO 10 mg Filmtabletten	10	St	7572633
XARELTO 10 mg Filmtabletten	10	St	7536850
XARELTO 10 mg Filmtabletten	10	St	10852626
XARELTO 10 mg Filmtabletten	10	St	10743771
XARELTO 10 mg Filmtabletten	10	St	10381894
XARELTO 10 mg Filmtabletten	10	St	10764520
XARELTO 10 mg Filmtabletten	30	St	5995080
XARELTO 10 mg Filmtabletten	30	St	6410420
XARELTO 10 mg Filmtabletten	30	St	7799029
XARELTO 10 mg Filmtabletten	30	St	5459513
XARELTO 10 mg Filmtabletten	30	St	9777888
XARELTO 10 mg Filmtabletten	30	St	5748766
XARELTO 10 mg Filmtabletten	30	St	7572662
XARELTO 10 mg Filmtabletten	30	St	7536927
XARELTO 10 mg Filmtabletten	30	St	6454481
XARELTO 10 mg Filmtabletten	30	St	10402662
XARELTO 10 mg Filmtabletten	30	St	10852632
XARELTO 10 mg Filmtabletten	30	St	10339455
XARELTO 10 mg Filmtabletten	30	St	10381902
XARELTO 10 mg Filmtabletten	30	St	11617270

XARELTO 10 mg Filmtabletten	30	St	11565001
XARELTO 10 mg Filmtabletten	100	St	5995097
XARELTO 10 mg Filmtabletten	10X10	St	9941276
XARELTO 15 mg Filmtabletten	14	St	8461344
XARELTO 15 mg Filmtabletten	14	St	10101682
XARELTO 15 mg Filmtabletten	14	St	10058590
XARELTO 15 mg Filmtabletten	14	St	10012139
XARELTO 15 mg Filmtabletten	14	St	10852649
XARELTO 15 mg Filmtabletten	14	St	10297679
XARELTO 15 mg Filmtabletten	14	St	10853560
XARELTO 15 mg Filmtabletten	14	St	10381919
XARELTO 15 mg Filmtabletten	14	St	10999312
XARELTO 15 mg Filmtabletten	14	St	11015708
XARELTO 15 mg Filmtabletten	14	St	10964153
XARELTO 15 mg Filmtabletten	28	St	8461350
XARELTO 15 mg Filmtabletten	28	St	9724515
XARELTO 15 mg Filmtabletten	28	St	4369423
XARELTO 15 mg Filmtabletten	28	St	10058609
XARELTO 15 mg Filmtabletten	28	St	10012145
XARELTO 15 mg Filmtabletten	28	St	10072093
XARELTO 15 mg Filmtabletten	28	St	10852655
XARELTO 15 mg Filmtabletten	28	St	10393650
XARELTO 15 mg Filmtabletten	28	St	10948987
XARELTO 15 mg Filmtabletten	28	St	10381925
XARELTO 15 mg Filmtabletten	28	St	7605019
XARELTO 15 mg Filmtabletten	28	St	11724729
XARELTO 15 mg Filmtabletten	42	St	8461404
XARELTO 15 mg Filmtabletten	42	St	9724521
XARELTO 15 mg Filmtabletten	42	St	10102144
XARELTO 15 mg Filmtabletten	42	St	10012151
XARELTO 15 mg Filmtabletten	42	St	10393667
XARELTO 15 mg Filmtabletten	42	St	4369452
XARELTO 15 mg Filmtabletten	42	St	10200906
XARELTO 15 mg Filmtabletten	42	St	10948970
XARELTO 15 mg Filmtabletten	42	St	10381931
XARELTO 15 mg Filmtabletten	42	St	10964176
XARELTO 15 mg Filmtabletten	42	St	10999329
XARELTO 15 mg Filmtabletten	42	St	10852661
XARELTO 15 mg Filmtabletten	42	St	11565018
XARELTO 15 mg Filmtabletten	98	St	8461367
XARELTO 15 mg Filmtabletten	98	St	9724538
XARELTO 15 mg Filmtabletten	98	St	10132139
XARELTO 15 mg Filmtabletten	98	St	10005926
XARELTO 15 mg Filmtabletten	98	St	10012168
XARELTO 15 mg Filmtabletten	98	St	7089598
XARELTO 15 mg Filmtabletten	98	St	10762403
XARELTO 15 mg Filmtabletten	98	St	10072101

XARELTO 15 mg Filmtabletten	98	St	10852678
XARELTO 15 mg Filmtabletten	98	St	10393696
XARELTO 15 mg Filmtabletten	98	St	4369475
XARELTO 15 mg Filmtabletten	98	St	10200912
XARELTO 15 mg Filmtabletten	98	St	10743794
XARELTO 15 mg Filmtabletten	98	St	10381948
XARELTO 15 mg Filmtabletten	98	St	10999335
XARELTO 15 mg Filmtabletten	98	St	11096606
XARELTO 15 mg Filmtabletten	98	St	11864962
XARELTO 15 mg Filmtabletten	98	St	11559348
XARELTO 15 mg Filmtabletten	100	St	9333393
XARELTO 15 mg Filmtabletten	10X10	St	9941282
XARELTO 20 mg Filmtabletten	14	St	8461410
XARELTO 20 mg Filmtabletten	14	St	10106863
XARELTO 20 mg Filmtabletten	14	St	10057490
XARELTO 20 mg Filmtabletten	14	St	10012174
XARELTO 20 mg Filmtabletten	14	St	10852684
XARELTO 20 mg Filmtabletten	14	St	10297685
XARELTO 20 mg Filmtabletten	14	St	10853577
XARELTO 20 mg Filmtabletten	14	St	10381954
XARELTO 20 mg Filmtabletten	14	St	10964182
XARELTO 20 mg Filmtabletten	14	St	10999341
XARELTO 20 mg Filmtabletten	14	St	11015714
XARELTO 20 mg Filmtabletten	28	St	8461427
XARELTO 20 mg Filmtabletten	28	St	9724544
XARELTO 20 mg Filmtabletten	28	St	10106886
XARELTO 20 mg Filmtabletten	28	St	4369481
XARELTO 20 mg Filmtabletten	28	St	10057509
XARELTO 20 mg Filmtabletten	28	St	10012180
XARELTO 20 mg Filmtabletten	28	St	10072118
XARELTO 20 mg Filmtabletten	28	St	10852690
XARELTO 20 mg Filmtabletten	28	St	10393638
XARELTO 20 mg Filmtabletten	28	St	10318631
XARELTO 20 mg Filmtabletten	28	St	10381983
XARELTO 20 mg Filmtabletten	28	St	7605025
XARELTO 20 mg Filmtabletten	28	St	10999358
XARELTO 20 mg Filmtabletten	98	St	8461433
XARELTO 20 mg Filmtabletten	98	St	9724550
XARELTO 20 mg Filmtabletten	98	St	10106892
XARELTO 20 mg Filmtabletten	98	St	10005932
XARELTO 20 mg Filmtabletten	98	St	10012197
XARELTO 20 mg Filmtabletten	98	St	7089606
XARELTO 20 mg Filmtabletten	98	St	10762426
XARELTO 20 mg Filmtabletten	98	St	10072124
XARELTO 20 mg Filmtabletten	98	St	10852709
XARELTO 20 mg Filmtabletten	98	St	10393644
XARELTO 20 mg Filmtabletten	98	St	4369498

XARELTO 20 mg Filmtabletten	98	St	10200929
XARELTO 20 mg Filmtabletten	98	St	10743802
XARELTO 20 mg Filmtabletten	98	St	10382008
XARELTO 20 mg Filmtabletten	98	St	10999364
XARELTO 20 mg Filmtabletten	98	St	11096612
XARELTO 20 mg Filmtabletten	98	St	11559354
XARELTO 20 mg Filmtabletten	100	St	9333401
XARELTO 20 mg Filmtabletten	10X10	St	9941299

Table 5 – Definition of types of AF

Type of AF	ICD-10-GM code
Paroxysmal	I48.0
Persistent	I48.1
Permanent	I48.2
Typical	I48.3
Atypical	I48.4
Unknown	I48.9

Table 6 – Definition of primary and secondary outcomes

Outcome parameter	ICD-10 GM code	
Primary effectiveness: ischemic stroke	I630, I631, I632, I633, I634, I635, I636, I638, I639	
Primary safety: Intracranial hemorrhage (ICH)	I60.0, I60.1, I60.2, I60.3, I60.4, I60.5, I60.6, I60.7, I60.8, I60.9, I61.0, I61.1, I61.2, I61.3, I61.4, I61.5, I61.6, I61.8, I61.9, I62.00, I62.01, I62.02, I62.09, I62.1, I62.9	
Secondary	combined endpoint cerebral benefit	ischemic stroke and ICH
	systemic embolism (SE) (effectiveness)	I26, I260, I269, I801, I802, I803, I809
	transient ischemic attack (TIA) (effectiveness)	G45.8, G45.9
	combined endpoint effectiveness	ischemic stroke, systemic embolism (SE) and transient ischemic attack (TIA)
	subarachnoid hemorrhage (safety)	I60.0, I60.1, I60.2, I60.3, I60.4, I60.5, I60.6, I60.7, I60.8, I60.9
	intracerebral hemorrhage (safety)	I61.0, I61.1, I61.2, I61.3, I61.4, I61.5, I61.6, I61.8, I61.9
	other and unspecified nontraumatic intracranial hemorrhage (safety)	I62.00, I62.01, I62.02, I62.09, I62.1, I62.9

Table 7 – Definition of stroke risk score CHADS₂ and CHA₂DS₂-VASc

Risk factor	CHADS₂ risk score value	CHA₂DS₂-VASc risk score value	ICD-10-GM code	Description
Heart failure	1	1	I50	Heart Failure
Hypertension	1	1	I10	Essential (primary) hypertension
Age 65-74 years	0	1	-	
Age ≥75 years	1	2	-	
Diabetes mellitus	1	1	E11/E10/ E12	Type 2 diabetes mellitus/ Type 1 diabetes mellitus/ Diabetes mellitus in combination with malnutrition Non-traumatic intracerebral hemorrhage/ Cerebral infarction/stroke/ Sequelae of cerebrovascular disease/ Other venous embolism and thrombosis/ Transient cerebral ischemic attacks and related syndromes/ Arterial embolism and thrombosis/ Acute vascular disorders of intestine/ Ischemia and infarction of kidney/ Retinal vascular occlusions Acute myocardial infarction/ recurrent myocardial infarction/ Certain current complications following myocardial infarction/ Other peripheral vascular diseases
Stroke/TIA/embolism	2	2	I61/I63/I64/ I69/I82/G45 /I74/K55.0/ N28.0/H34	
Vascular disease (prior myocardial infarction/peripheral artery disease/aortic plaque)	0	1	I21/I22/I23/ I73	
Female gender	0	1	-	

Table 8 – Comorbidities included in the Charlson Comorbidity Index (CCI) and modified comorbidity index

Conditions	ICD-10 GM code	Assigned weights CCI	Assigned weights modified comorbidity index
Myocardial Infarction	I21, I22, I252	1	1
Congestive heart failure	I43, I50, I099, I110, I130, I132, I255, I420, I425, I 426, I427, I428, I429, P290	1	0
Peripheral vascular disease	I70, I71, I731, I738, I739, I771, I790, I792, K551, K558, K559, Z958, Z959	1	1
Cerebrovascular disease	G45, G46, I60, I61, I62, I63, I64, I65, I66, I67, I68, I69, H340	1	0
Dementia	F00, F01, F02, F03, G30, F051, G311	1	1
Chronic pulmonary disease	J40, J41, J42, J43, J44, J45, J46, J47, J60, J61, J62, J63, J64, J65, J66, J67, I278, I279, J684, J701, J703	1	1
Connective tissue disease	M05, M32, M33, M34, M06, M315, M351, M353, M360	1	1
Ulcer disease	K25, K26, K27, K28	1	1
Mild liver disease	B18, K73, K74, K700, K701, K702, K703, K709, K717, K713, K714, K715, K760, K762, K763, K764, K768, K769, Z944	1	0
Diabetes	E100, E101, E106, E108, E109, E110, E111, E116, E118, E119, E120, E121, E126, E128, E129, E130, E131, E136, E138, E139, E140, E141, E146, E148, E149	1	1
Hemiplegia	G81, G82, G041, G114, G801, G802, G830, G831, G832, G833, G834, G839	2	2
Moderate or severe renal disease	N18, N19, N052, N053, N054, N055, N056, N057, N250, I120, I131, N032, N033, N034, N035, N036, N037, Z490, Z491, Z492, Z940, Z992	2	0
Diabetes with end organ damage	E102, E103, E104, E105, E107, E112, E113, E114, E115, E117, E122, E123, E124, E125, E127, E132, E133, E134, E135, E137, E142, E143, E144, E145, E147	2	2

Any tumor	C00, C01, C02, C03, C04, C05, C06, C07, C08, C09, C10, C11, C12, C13, C14, C15, C16, C17, C18, C19, C20, C21, C22, C23, C24, C25, C26, C30, C31, C32, C33, C34, C37, C38, C39, C40, C41, C43, C45, C46, C47, C48, C49, C50, C51, C52, C53, C54, C55, C56, C57, C58, C60, C61, C62, C63, C64, C65, C66, C67, C68, C69, C70, C71, C72, C73, C74, C75, C76, C81, C82, C83, C84, C85, C88, C90, C91, C92, C93, C94, C95, C96, C97	2	2
Moderate or severe liver disease	K704, K711, K721, K729, K765, K766, K767, I850, I859, I864, I982	3	0
Metastatic solid tumor or AIDS	C77, C78, C79, C80, B20, B21, B22, B24	6	6

Table 9 – Operationalization HAS-BLED Score

Criteria	ICD-10 GM code
Hypertension	I10.*, I11.*, I12.*, I13.*, I14.*, I15.*
Renal disease	N18.*, N19.*
Cirrhosis	K70.3, K71.7, K74.*
Stroke	I63.*
Major bleeding event	Primary or secondary hospital discharge of ICD-10 codes as listed in Table 11
Alcohol use	F10.*
Non-steroidal anti-inflammatory drug	M01A*
Antiplatelet agents	B01AC*
Age >65	

Table 10 – Definition of comorbidities

Comorbidity	ICD-10-GM code / OPS Code
Hemorrhagic diathesis due to anticoagulants and antibodies	D68.3
Coagulopathy, not specified	D68.9
Hyperthyroidism	E05
Diabetes mellitus	E10-E14
Hyperlipidemia	E78.0-E78.5
Cerebral transitory ischemia and related problems	G45
Essential hypertension	I10
Angina pectoris	I20
Myocardial infarction	I21-I22
Other acute ischaemic heart disease	I24
Chronic ischaemic heart disease	I25
Pulmonary embolisms	I26
Heart failure	I50
Intracerebral hemorrhage	I61
Other non-traumatic intracranial bleeding	I62
Cerebral infarction	I63
Stroke, not referred to as bleeding or infarction	I64
Hemorrhage or intracranial bleeding or cerebral infarction or stroke	I61-I64
Peripheral vascular disease, not specified	I73.9
Embolism and thrombosis of unspecified artery	I74.9
Deep thrombosis on leg and pelvic veins	I80-I82 without I80.0
Functional dyspepsia	K30
Hepatic insufficiency	K72
Renal insufficiency	N17-N18
Chronic renal disease, stage 1	N18.1
Chronic renal disease, stage 2	N18.2
Chronic renal disease, stage 3	N18.3
Chronic renal disease, stage 4	N18.4
Chronic renal disease, stage 5	N18.5
Cancer	C00-C97
Gastrointestinal bleeding*	K92.0.-K92.2
Dialysis	Z49.0, Z49.1, Z49.2
Hip or knee replacement procedure	OPS 5820, OPS 5821, OPS 5822, OPS 5823

Table 11 – Definition of major bleeding events for HAS-BLED Score

Primary or secondary hospital discharge diagnosis ICD-10-GM code	ICD-10-GM code
Conjunctival haemorrhage	H11.3
Otorrhagia	H92.2
Oesophageal varices with bleeding	I85.0
Oesophageal varices without bleeding in diseases classified elsewhere with bleeding	I98.21
Other specified diseases of oesophagus	K22.8
Gastric ulcer with bleeding	K25.0, K25.2, K25.4, K25.6
Duodenal ulcer with bleeding	K26.0, K26.2, K26.4, K26.6
Peptic ulcer, site unspecified with bleeding	K27.0, K27.2, K27.4, K27.6
Gastrojejunal ulcer with bleeding	K28.0, K28.2, K28.4, K28.6
Acute haemorrhagic gastritis	K29.0
Other specified diseases of stomach and duodenum and bleeding	K31.82
Angiodysplasia of colon with bleeding	K55.22
Diverticular disease of small intestine with perforation and abscess and bleeding	K57.01, K57.03
Diverticular disease of small intestine without perforation and abscess and bleeding	K57.11, K57.13
Diverticular disease of large intestine with perforation and abscess and bleeding	K57.21, K57.23
Diverticular disease of large intestine without perforation or abscess with bleeding	K57.31, K57.33
Diverticular disease of both small and large intestine with perforation and abscess and bleeding	K57.41, K57.43
Diverticular disease of both small and large intestine without perforation or abscess with bleeding	K57.51, K57.53
Diverticular disease of intestine, part unspecified, with perforation and abscess and bleeding	K57.81, K57.83
Diverticular disease of intestine, part unspecified, without perforation or abscess with bleeding	K57.91, K57.93
Haemorrhage of anus and rectum	K62.5
Haemoperitoneum	K66.1
Haematemesis	K92.0
Melaena	K92.1
Gastrointestinal haemorrhage, unspecified	K92.2
Recurrent and persistent haematuria	N02.0, N02.1, N02.2, N02.3, N02.4, N02.5, N02.6, N02.7, N02.8, N02.9
Congestion and haemorrhage of prostate	N42.1
Haematosalpinx	N83.6
Haematometra	N85.7
Haematocolpos	N89.7
Other abnormal uterine and vaginal bleeding	N93.0, N93.8, N93.9
Postmenopausal bleeding	N95.0

Haemorrhage from respiratory passages	R04.0, R04.1, R04.2, R04.8, R04.9
Spontaneous ecchymoses	R23.3
Unspecified haematuria	R31
Haemorrhage, not elsewhere classified	R58
Open wound of vagina and vulva	S31.4
Acute posthaemorrhagic anaemia	D62
Hyphaema	H21.0
Cyst of iris, ciliary body and anterior chamber	H31.3, H31.30, H31.31
Retinal haemorrhage	H35.6
Vitreous haemorrhage	H43.1
Vitreous haemorrhage in diseases classified elsewhere	H45.0
Haemopericardium, not elsewhere classified	I31.2
Haemothorax	J94.2
Gastro-oesophageal laceration-haemorrhage syndrome	K22.6

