8.2 Secondary objective(s)

The secondary objectives of this study are:

- To assess the cerebral benefit in patients treated with Rivaroxaban compared to patients treated with Phenprocoumon. The combined endpoint is defined as the occurrence of a hospitalization with one of the following diagnoses
 - ischemic stroke
 - ICH
- To assess the real world effectiveness defined as the combined endpoint of ischemic stroke, systemic embolism (SE) and transient ischemic attack (TIA) in patients treated with Rivaroxaban compared to patients treated with Phenprocoumon. The components of this combined endpoint will also be analyzed separately. The composite event is defined as the occurrence of a hospitalization with one of the following diagnoses
 - ischemic stroke
 - systemic embolism
 - TIA

9. Research methods

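### The systemic embolism row of Table 6 contains only pulmonary embolism and deep vein thrombosis codes and omits I74, so the SE endpoint and the SE part of the effectiveness composite count venous events

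*Protocol*

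**What the plan says.** Section 8.2 makes a composite of ischemic stroke, SE and TIA a secondary objective and promises separate analysis of its components. Table 33 has a row for SE with its own hazard ratio. Section 9.3.3 accepts a primary or a secondary hospital discharge diagnosis as an event and sends the reader to Table 6 for the codes.

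In Table 6 (Annex 2) the SE row reads "I26, I260, I269, I801, I802, I803, I809". The composite row of that table refers back to SE by name, so it takes over the same list. No other outcome code list for SE appears in the protocol.

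Table 6 is also the reference for the prior-event criterion in section 9.2.2, which is marked as applying to a sensitivity analysis.

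Section 9.7 states that no separate statistical analysis plan will be written.

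**The concern.** The codes do not match the name of the outcome. The protocol elsewhere attaches the names pulmonary embolism and deep vein thrombosis to these codes, and it has arterial embolism codes available that were not used in this row.

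Three results are at stake:

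- **The SE hazard ratio.** It would compare the drugs on VTE admissions while being labelled as systemic embolism.
- **The effectiveness composite.** It is meant to describe stroke prevention in atrial fibrillation. A patient admitted with, or additionally coded for, a pulmonary embolism or deep vein thrombosis would count as an event, and a patient admitted with a limb-artery embolism would not.
- **The prior-event criterion.** Its SE part would pick out patients with earlier VTE and pass over those with earlier arterial embolism.

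With no later analysis plan foreseen, the row would be programmed as it stands.

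**Working it through.** The protocol gives no figure to reproduce here. The check compares code lists within the protocol.

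**Step 1. Label each SE code using the protocol's own tables.**

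| SE entry in Table 6 | Matching entry in Table 10 | Label in Table 10 |
|---|---|---|
| I26, I26.0, I26.9 | I26 | "Pulmonary embolisms" |
| I80.1, I80.2, I80.3, I80.9 | "I80-I82 without I80.0" | "Deep thrombosis on leg and pelvic veins" |

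Count: 3 pulmonary embolism entries + 4 deep vein thrombosis entries = 7 of 7. Section 9.2.2 groups the same two conditions as VTE when it excludes patients who had them in the 60 days before index, and it also points to Table 10.

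**Step 2. Look for arterial codes.** The row for stroke, TIA and embolism in Table 7 lists I61, I63, I64, I69, I82, G45, I74, K55.0, N28.0 and H34. Its description includes "Arterial embolism and thrombosis/ Acute vascular disorders of intestine", followed by kidney infarction and retinal vascular occlusion. Table 10 carries I74.9 as embolism of an unspecified artery. The overlap between the SE row of Table 6 and this Table 7 row is 0 of 7 codes. I74 is not in the SE row at any level.

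**Step 3. Ask whether a venous meaning was intended.** The baseline list in section 9.3.1 has an item for earlier systemic embolism outside the central nervous system, and separate items for DVT and pulmonary embolism. The protocol therefore treats them as different conditions. No section says that SE is to include venous events. A deliberately broad definition would add venous codes to arterial ones, whereas this row has venous codes only.

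**Step 4. Trace where the row is used.**

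- SE as a single outcome (section 8.2, Table 33): all codes affected.
- Effectiveness composite: one of three components affected. Ischemic stroke (I63.x) and TIA (G45.8, G45.9) are coded as named.
- Prior-event criterion (sections 9.2.2 and 9.7.1.2): only its SE part affected. Section 9.2.2 lists it as an exclusion for the sensitivity analysis, while section 9.7.1.2 says such patients are included in a separate analysis. In either direction, the SE part selects on VTE history.
- Ischemic stroke, ICH, the cerebral-benefit composite and the power tables in section 9.5: the SE row is not used.

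**Step 5. Size.** Ignoring overlap of first events, the venous share of composite events would be VTE rate ÷ (stroke rate + TIA rate + VTE rate). Section 9.5 gives ischemic stroke rates from 0.0054 to 0.0134 depending on the source study. The protocol gives no TIA, VTE or SE rate, so the share cannot be calculated from it.

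**The case against.** The best counter-argument concerns reach. The SE row feeds one secondary component and one secondary composite, and the main answer of the study does not depend on it. That stands. A reader might infer that the whole composite measures the wrong disease, but its stroke and TIA components are coded correctly and the fault lies in the SE component alone.

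A second argument is that the protocol itself is loose about venous codes: the Table 7 embolism row includes I82, described as other venous embolism and thrombosis. This is true, and it means that the Table 7 row should not be copied whole. It does not rescue Table 6, because Table 7 at least contains I74 and Table 6 contains no arterial code.

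Third, only I74 is expressly called arterial embolism in Table 7. K55.0, N28.0 and H34 carry broader descriptions (intestinal vascular disorders, kidney ischemia and infarction, retinal occlusion). This also stands. Their absence from the SE row is a matter of definition to settle, while the absence of I74 conflicts with the name of the outcome.

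Fourth, the effect of the prior-event criterion should not be overstated. It also covers prior stroke and TIA, and VTE in the 60 days before index is already excluded from the cohort.

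**Conclusion.** The point holds from the protocol's own tables: 7 of 7 SE codes are venous and I74 is missing. The SE hazard ratio as specified is a VTE hazard ratio. The effectiveness composite is contaminated in its SE component, and the SE part of the prior-event criterion selects on VTE history. The conclusion assumes only that SE carries the meaning implied by section 9.3.1, distinct from DVT and pulmonary embolism.

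Two further inferences are tempting but unsupported. One is a percentage of composite events that would be venous, or a direction of bias in the hazard ratio; both need rates that the protocol does not give. The other is that the SE count will fall after correction, which would need an arterial embolism rate, also absent. Nor does the protocol say that the baseline item on earlier systemic embolism uses the Table 6 row, so an error there cannot be claimed.

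**What to change.** In Table 6, remove I26 and I80.x from the SE row and enter arterial embolism codes, at least I74.x. Decide explicitly whether K55.0, N28.0 and H34 belong, by reconciling the row with Table 7 and leaving out its venous code I82. State that the corrected list applies to the SE outcome, the effectiveness composite and the SE part of the prior-event criterion. If VTE is of interest, report I26 and I80.x as a separate outcome under that name.

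The cost is one row of a code list and a sentence on where it applies. Sample size and power are untouched. The change should be in the final protocol before any outcome is tabulated, so that it cannot look data-driven. The milestones put the final protocol and the start of analyses on the same date (15 October 2016), which leaves no interval between them for a later correction.

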Hypertension	categorical	Ambulatory verified diagnoses in the four quarters prior to the index quarter as well as primary and secondary hospital discharge diagnoses within the 365 days before or on the index date will be used assess whether patients suffered from hypertension. Hypertension will be defined using the ICD-10 GM code I10.*.
Congestive heart failure	categorical	Ambulatory verified diagnoses in the four quarters prior to the index quarter as well as primary and secondary hospital discharge diagnoses within the 365 days before or on the index date will be used assess whether patients suffered from congestive heart failure. Congestive heart failure will be defined using the ICD-10 GM code I50.*.

Atherosclerosis of arteries of extremities	categorical	Ambulatory verified diagnoses in the four quarters prior to the index quarter as well as primary and secondary hospital discharge diagnoses within the 365 days before or on the index date will be used assess whether patients suffered from peripheral vascular disease. Peripheral vascular disease will be defined using the ICD-10 GM code I70.2.
Ischemic stroke or TIA during baseline	categorical	Ambulatory verified diagnoses in the four quarters prior to the index quarter as well as primary and secondary hospital discharge diagnoses within the 365 days before or on the index date will be used assess whether patients suffered from ischemic stroke or TIA. Ischemic stroke or TIA will be defined using the ICD-10 GM code I63, I64, G45.9 and G45.8.
Coronary heart disease	categorical	Ambulatory verified diagnoses in the four quarters prior to the index quarter as well as primary and secondary hospital discharge diagnoses within the 365 days before or on the index date will be used assess whether patients suffered from coronary heart disease. Coronary heart disease will be defined using the ICD-10 GM code I20*(angina pectoris), I24.*(other acute ischemic heart diseases) and I25* (chronic ischaemic heart disease).
Liver disease		
Mild liver disease	categorical	Ambulatory verified diagnosis in the four quarters prior to the index quarter as well as primary and secondary hospital discharge diagnoses within the 365 days before or on the index date will be used assess whether patients suffered from a mild liver disease. Mild liver disease will be defined using the ICD-10 GM codes according to the Charlson Comorbidity Index (Table 8).

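### I64 counts as stroke at baseline but is in no outcome, so the cerebral-benefit composite and the prior-event exclusion both leave it out; the G45 range also differs between tables

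*Protocol*

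**What the plan says.** **Outcomes (Annex 2, Table 6).** Ischemic stroke is "I630, I631, I632, I633, I634, I635, I636, I638, I639". ICH is I60.x, I61.x and I62.x. The row "transient ischemic attack (TIA) (effectiveness" carries G45.8 and G45.9. Cerebral benefit is "ischemic stroke and ICH", and the effectiveness composite is "ischemic stroke, systemic embolism (SE) and transient ischemic attack (TIA". I64 is in none of these rows.

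**Baseline.** For the Table 2 covariate on prior events, Section 9.3.1 states: "Ischemic stroke or TIA will be defined using the ICD-10 GM code I63, I64, G45.9 and G45.8". The stroke/TIA/embolism item of the two stroke risk scores (Table 7) is worth 2 points, and its code list begins "I61/I63/I64/ I69/I82/G45". Table 7 describes G45 as "Transient cerebral ischemic attacks and related syndromes". Table 10 lists all of G45 as "Cerebral transitory ischemia and related problems". It also gives I64 a row of its own as stroke without a stated type, and includes I64 in a combined I61 to I64 row.

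**Rules that depend on Table 6.** Section 9.2.2 excludes, for a sensitivity analysis, patients with a prior event from the combined endpoints and refers to Table 6 for the list. Section 9.3.2 adds hospital days to exposure time and treats only outcome-related admissions as events. Section 9.7 says there will be no separate SAP, so Table 6 is the working definition.

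**The concern.** A stroke that the hospital did not type as bleeding or infarction is a prior stroke if it falls before the index date and nothing if it falls after. For an endpoint named ischemic stroke, a narrow list can be a deliberate choice. For a composite covering both ischemic stroke and ICH, the missing type does not matter, because the event qualifies either way.

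Two consequences follow. The composite loses qualifying events, in a study whose rationale (Section 7) blames low event numbers for earlier non-significant results. And the cohort meant to be free of prior events can still contain patients whom Table 2 records as having had an ischemic stroke or TIA.

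The G45 difference is a second and weaker inconsistency. An admission under another G45 code scores in Table 7 as stroke/TIA/embolism history but is not a TIA event after index. No reason is given for either difference.

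**Working it through.** No figure in the Protocol depends on these code lists, so there is none to reproduce. The check is a comparison of the lists.

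| Place | Stroke codes | G45 codes | Use |
|---|---|---|---|
| Table 6 | I63.x; I60–I62 for ICH | G45.8, G45.9 | outcomes; prior-event exclusion |
| Table 2 | I63, I64 | G45.8, G45.9 | covariate for prior ischemic stroke or TIA |
| Table 7 | I61, I63, I64, I69 | all | 2 points in both scores |
| Table 8 | I60–I69 | all | Charlson cerebrovascular category |
| Table 9 | I63 only | none | HAS-BLED stroke item |
| Table 10 | I61–I64, singly and combined | all | comorbidities |

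**Step 1, I64 as an outcome.** The union of Table 6 stroke and ICH codes is I60, I61, I62 and I63. I64 lies outside it. By Table 10's own label, an I64 stroke is one whose type was not recorded. If it was an infarction it belongs under ischemic stroke; if it was a bleed it belongs under ICH. Cerebral benefit contains both, so the event qualifies in either case and is still not counted.

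**Step 2, follow-up after an I64 admission.** The admission is not outcome-related under Table 6. Section 9.3.2 therefore adds its days to exposure, and the patient continues as event-free.

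**Step 3, prior events.** The exclusion removes Table 6 events only. If it is applied to the same diagnosis sources as Table 2, everyone left has no prior I63, G45.8 or G45.9, so the Table 2 covariate can be positive only through I64. Anyone for whom it is positive is recorded as having a prior ischemic stroke or TIA inside a cohort defined by having none. (Section 9.2.2 attaches this exclusion to the sensitivity analysis, while Section 9.7.1.2 describes the sensitivity analysis as including such patients. The point holds for whichever cohort excludes them.)

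**Step 4, G45.** The TIA codes in Table 2 and Table 6 are identical. The wider range appears only in Tables 7, 8 and 10. Cerebral benefit has no TIA component, so G45 cannot affect it. Only TIA and the effectiveness composite are open to this question.

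**Step 5, size.** The Protocol gives no frequency for I64 or for other G45 codes. The standard error of a log hazard ratio scales with 1/√events, so losing a fraction f of events equally in both arms multiplies it by 1/√(1 − f). As an assumption only, suppose I64 would be 1% to 5% of the full composite:

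- f = 0.01: 1/√0.99 = 1.005
- f = 0.05: 1/√0.95 = 1.026

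On that assumed range the loss of precision is about 0.5% to 2.6%.

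**The case against.** **I64.** Leaving a stroke of unknown type out of an endpoint called ischemic stroke protects specificity, and baseline use of I64 is not uniform either, since HAS-BLED uses I63 only. This stands, and it is why the primary endpoint should stay as it is. It does not carry over to a composite that includes both types.

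**Component consistency.** Cerebral benefit is the union of the two primary endpoints, and Section 4 says the single events of all combined endpoints will be analyzed. Adding I64 would put events in the composite that belong to neither component. The objection is fair and is met by reporting I64 as a component of its own.

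**TIA.** A reader might infer that the Protocol treats all of G45 as TIA at baseline and that the outcome therefore misses TIAs. The documents do not support that. The dedicated Table 2 covariate uses exactly the outcome's two codes. Tables 7 and 10 label the whole category as TIA plus related conditions. Table 7's item is a broad risk-score item that also covers embolism, and nothing in the Protocol says what the other G45 subcodes contain. A broad covariate beside a narrower outcome can be a deliberate choice.

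A reader might also assume that 10% to 40% of TIA admissions carry other G45 codes and obtain a standard error larger by 1/√0.9 = 1.05 to 1/√0.6 = 1.29. The arithmetic is right but the input is not in the documents. It would apply to TIA alone; the effect on the effectiveness composite, which also counts stroke and systemic embolism, would be smaller.

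**Conclusion.** The I64 point holds. Table 6 omits a code that Tables 2, 7 and 10 treat as stroke, the omission has no stated reason, and specificity cannot justify it for cerebral benefit. The prior-event exclusion inherits the gap. The G45 difference between Tables 2/6 and Tables 7/8/10 is real but shows only that the lists are not aligned; how many TIA events are missed, if any, is unknown.

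This is a low-cost improvement and not a threat to the main result. Both primary endpoints keep their definitions, and the power table in Section 9.5 is untouched. Nothing in the documents indicates a difference between arms, so no direction of bias is claimed. The size of the effect cannot be derived from the Protocol, and the percentages above rest on assumed shares. The conclusion rests on Table 10's description of I64 and on the exclusion being applied literally from Table 6.

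**What to change.** 1. Add I64 to the cerebral-benefit composite in Table 6 and show it as its own component in the result tables (Tables 32 to 34).
2. Add I64 to the list used for the prior-event exclusion in Section 9.2.2.
3. Keep the I63-only primary endpoint and add a sensitivity analysis of ischemic stroke with I63 plus I64.
4. Keep G45.8 and G45.9 as the TIA outcome and add a sensitivity analysis of TIA and the effectiveness composite with the broader G45 list, leaving out G45.4. The Protocol does not describe the subcodes, so the coding team should confirm this list against the classification.
5. State in one sentence why the G45 range in Tables 7, 8 and 10 is wider than in Tables 2 and 6.

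The cost is a code-list edit and a few extra model runs on the same hospital data. Some added codes may be less specific, so counts under the present Table 6 definitions should be shown alongside.
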